4.4 RANDOMIZATION

Quantitative Health Sciences has designed a randomization scheme which will be used to make the treatment assignments for the study subjects. This randomization plan is included in the appendix as 11.7.

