3 INVESTIGATIONAL PLAN

3.1 SUMMARY OF STUDY DESIGN

This is a single site, randomized, open-label, two arm, crossover, study of subject productivity improvement and satisfaction with migraine treatment using Treximet™ vs usual triptan.

This study will recruit 60 patients who are employed in a paying job, who have episodic migraine (<15 days/month), who are using acute care triptan monotherapy for their migraine (excluding combinations of any sort, such as acetaminophen [APAP] and non-steroidals [NSAIDs]) and who have no contraindications to triptan or NSAID use.

In one arm of the study, patients will treat 3 work day migraines with their usual triptan and in the other arm of the study the same patients will treat 3 work day migraines with Treximet. The medication that they use in the first arm of the study is determined by randomization. They will maintain headache diaries for the duration of the study and fill out the WPAI after each work day migraine. After treating 3 work day migraines, they will also fill out CORS Part 1 and Migraine-ACT.

Between the completion of the 3rd migraine attack treatment, and the start of the second treatment arm, there will be a minimum of a 48 hour washout period and an office visit.

In the second arm, after cross over to the other treatment, the sixty patients will maintain headache diaries, treat 3 attacks during any day in which they are scheduled to work, and fill out the WPAI after each attack. Additionally, after 3 attacks are treated, they will fill out CORS Part 1, CORS Part 2 and Migraine-ACT. This second arm differs from arm one in that the subjects will treat their migraines with the other medication from that assigned in the first arm.

Subject participation will last approximately 3 months, depending on the days needed to treat migraines during the workday according to protocol.

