4. SUBJECT SELECTION

4.1 NUMBER OF SUBJECTS

This study will enroll 60 subjects for participation. There are no other sites for this study.

The sample size was chosen to be a sufficient number to assess the effect of Treximet on the WPAI using a crossover design in which patients will serve as their own controls.

Based on previous GSK studies on Treximet utilizing the WPAI, the effect size between Treximet and usual triptan care is expected to be small. In those studies, comparisons of Treximet to placebo yielded differences of 0.4 to 1.4. For this study, a one-point WPAI difference between Treximet and triptan is assumed to be clinically meaningful. Furthermore, the GSK Treximet studies were parallel designs with standard deviations ranging from 2.5 to 3.5. To account for the correlation from patients acting as their own controls in this crossover design, a standard deviation of the difference equal to 2.5 is assumed. Under these assumptions, a total sample of 60, with 30 in each sequence, would power the study at 86%.

4.2 INCLUSION CRITERIA:

A subject will be eligible to participate in this study if all of the following criteria apply:

1. subject is 18 years or older at screening
2. subject has a history of migraine greater than 1 year
3. subject has been diagnosed with migraine before age 50
4. subject is an employed person (is paid wages for his/her work)

5. subject has diagnosis of episodic migraine, by IHS criteria
6. subject uses triptan monotherapy as the primary migraine abortive treatment
7. subject is not pregnant or nursing

4.3 EXCLUSION CRITERIA:

A subject will not be eligible to participate in this study if any of the following criteria apply:

1. subject is less than 18 years of age at screening
2. subject does not have history of migraine greater than 1 year
3. subject was diagnosed with migraine after age 50
4. subject is not currently employed
5. subject does not have diagnosis of episodic migraine
6. subject does not use triptan monotherapy as primary migraine abortive treatment
7. subject is pregnant or nursing
8. subjects with a history of stroke, myocardial infarction (including vasospastic coronary artery disease [CAD] or cardiovascular thrombotic events)
9. subjects with gastrointestinal disease history to include ulcers, bleeding or perforations of the stomach or intestines
10. subjects with a history of significant renal or hepatic disease.

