5.3 STUDY DRUG SUPPLY

For the treatment period when the subjects are taking Treximet™, they will be dispensed a study drug bottle containing 3 Treximet™ tablets for initial dosing (1 tablet dose) of 3 migraines during the work day.

5.3.1 Treatment Assignment will be made according to the randomization schedule created by Quantitative Health Sciences at Cleveland Clinic.

5.3.2 Treatment will be open label.

5.3.3 For study product accountability, subjects will have documented dispensation of study product and will return study drug containers at the office visit following the Treximet™ treatment arm completion.

5.3.4 Subjects will record treatment use in study diaries for the treated migraine attacks.

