8.2 DESIGN AND DATA ANALYSIS CONSIDERATIONS

For the crossover design, there is a special need to identify if a carryover effect exists. For the primary outcome, WPAI score after last attack, the mean sequence sums will be compared with a 2-sample t-test (see Toutenburg in references pp. 344-346). If no significance is found, then the assumption will be that there is no carryover effect and treatment differences will be evaluated through a mixed model analysis. The model will include trial period, sequence (usual triptan f/b Treximet or Treximet f/b usual triptan) and treatment as fixed effects. If carryover does exist, then only the first trial period results will be used and a 2-sample t-test will be conducted to look for treatment differences. A sensitivity analysis will be performed in which WPAI scores from all 3 attacks will be included in the model. A second model will be created with the inclusion of an interaction term between treatment and pain level at time of dose.

Lost Workplace Productivity and Non-Work Activity Time - WPAI analysis

Subjects are to record the number of hours they miss from work due to migraine symptoms (WM), the number of hours they miss from routine activities outside of paid work due to migraine symptoms (RAM), the number of hours they continue to work while having migraine symptoms (WS), the number of hours they continue routine activities while having migraine symptoms (RAS), and how effective they are while continuing routine activities while having migraine symptoms (RAE). Lost workplace productivity (LWP) and lost activity time (LAT)

will be calculated as follows. The overall lost workplace productivity and activity time for the attack will be the sum of the two measures (LWP + LAT) where

$$LWP = WM + (WS \times [(100\% - WE)/100\%])$$

$$LAT = (RAM + (RAS \times [(100\% - RAE)/100\%]))$$

If the subject has indicated that work was not scheduled on a given diary, the LWP for that diary day will be 0 regardless of what information may have been filled out on the diary regarding WM, WS, or WE.

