APPENDIX 11.7

Randomization Table

Subject Order Entry	Sequence	First Period Treatment	Second Period Treatment
1	Treximet f/b Triptan	Treximet	Triptan
2	Treximet f/b Triptan	Treximet	Triptan
3	Triptan f/b Treximet	Triptan	Treximet
4	Treximet f/b Triptan	Treximet	Triptan
5	Triptan f/b Treximet	Triptan	Treximet
6	Treximet f/b Triptan	Treximet	Triptan
7	Triptan f/b Treximet	Triptan	Treximet
8	Triptan f/b Treximet	Triptan	Treximet
9	Treximet f/b Triptan	Treximet	Triptan
10	Triptan f/b Treximet	Triptan	Treximet
11	Triptan f/b Treximet	Triptan	Treximet
12	Treximet f/b Triptan	Treximet	Triptan
13	Triptan f/b Treximet	Triptan	Treximet
14	Treximet f/b Triptan	Treximet	Triptan
15	Treximet f/b Triptan	Treximet	Triptan
16	Triptan f/b Treximet	Triptan	Treximet
17	Triptan f/b Treximet	Triptan	Treximet
18	Treximet f/b Triptan	Treximet	Triptan
19	Treximet f/b Triptan	Treximet	Triptan
20	Triptan f/b Treximet	Triptan	Treximet
21	Triptan f/b	Triptan	Treximet

	Treximet		
22	Triptan f/b Treximet	Triptan	Treximet
23	Triptan f/b Treximet	Triptan	Treximet
24	Triptan f/b Treximet	Triptan	Treximet
25	Treximet f/b Triptan	Treximet	Triptan
26	Triptan f/b Treximet	Triptan	Treximet
27	Treximet f/b Triptan	Treximet	Triptan
28	Treximet f/b Triptan	Treximet	Triptan
29	Triptan f/b Treximet	Triptan	Treximet
30	Treximet f/b Triptan	Treximet	Triptan
31	Treximet f/b Triptan	Treximet	Triptan
32	Triptan f/b Treximet	Triptan	Treximet
33	Triptan f/b Treximet	Triptan	Treximet
34	Treximet f/b Triptan	Treximet	Triptan
35	Triptan f/b Treximet	Triptan	Treximet
36	Treximet f/b Triptan	Treximet	Triptan
37	Treximet f/b Triptan	Treximet	Triptan
38	Treximet f/b Triptan	Treximet	Triptan
39	Triptan f/b Treximet	Triptan	Treximet
40	Triptan f/b Treximet	Triptan	Treximet
41	Triptan f/b Treximet	Triptan	Treximet
42	Treximet f/b Triptan	Treximet	Triptan
43	Treximet f/b Triptan	Treximet	Triptan

44	Treximet f/b Triptan	Treximet	Triptan
45	Triptan f/b Treximet	Triptan	Treximet
46	Triptan f/b Treximet	Triptan	Treximet
47	Triptan f/b Treximet	Triptan	Treximet
48	Treximet f/b Triptan	Treximet	Triptan
49	Triptan f/b Treximet	Triptan	Treximet
50	Triptan f/b Treximet	Triptan	Treximet
51	Treximet f/b Triptan	Treximet	Triptan
52	Triptan f/b Treximet	Triptan	Treximet
53	Treximet f/b Triptan	Treximet	Triptan
54	Treximet f/b Triptan	Treximet	Triptan
55	Triptan f/b Treximet	Triptan	Treximet
56	Treximet f/b Triptan	Treximet	Triptan
57	Treximet f/b Triptan	Treximet	Triptan
58	Triptan f/b Treximet	Triptan	Treximet

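### The complete allocation list is printed in the protocol in order of entry, with no concealment step, so the next patient's sequence can be known before enrolment

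*Combined protocol and SAP*

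**What the plan says.** Section 4.4 assigns the design of the scheme to the statistics group, says it will be used to assign subjects, and continues: "This randomization plan is included in the appendix as 11.7". Appendix 11.7 is a plain table headed "Subject Order Entry", with rows 1 to 60 and the sequence and both period treatments in clear text.

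Section 5.3.1 says only this about how an assignment reaches a patient: "Treatment Assignment will be made according to the randomization schedule created by Quantitative Health Sciences at Cleveland Clinic". Section 5.3.2 adds: "Treatment will be open label". Section 4.1 confirms that there is a single site. The flow chart in section 6 marks informed consent, inclusion/exclusion and randomization at the same Visit 1.

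No section mentions envelopes, a call-in or web system, a list kept from recruiting staff, or release after eligibility is confirmed.

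Two analysis rules in section 8.2 depend on the sequence groups being comparable. For carryover, "the mean sequence sums will be compared with a 2-sample t-test". If that test is significant, "only the first trial period results will be used and a 2-sample t-test will be conducted". Migraine-ACT has an equivalent pair of rules.

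**The concern.** Concealment means that whoever decides on a patient's entry cannot know what that patient will be assigned. Here the plan itself publishes the answer. At one open-label site the running enrolment count is easy to follow, so the next row of the table is known. Some entry criteria call for judgement (significant renal or hepatic disease, uncontrolled hypertension), and the timing of a patient's entry is also open to choice.

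If patients with more disabling attacks drift towards one sequence, the sequence totals differ even with no carryover, and the pretest cannot tell the two apart. A significant pretest discards the second period and moves the conclusion to a first-period comparison between patients. The same difference in mix then biases that comparison.

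**Working it through.** **The list.** Counting Appendix 11.7 gives 60 entries, 30 Treximet-first and 30 triptan-first, which matches section 4.1. It is therefore the operative list and not a specimen. It shows no fixed balanced blocks (entries 20 to 24 are all triptan-first). Without the table, always guessing the sequence that is behind would be right for 35 of 60 entries (58%). With the table, all 60 are known.

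**The plan's own power figure.** Inputs from section 4.1: difference 1, SD of the within-patient difference 2.5, N = 60. The noncentrality is 1/(2.5/√60) = 3.098. A noncentral t with 58 df and two-sided alpha 0.05 (sidedness is not stated) gives 86.1%, against the stated 86%. Concealment does not alter this. The first-period fallback, 30 against 30, has standard error SD × √(2/30): 0.645 at SD 2.5 and 0.904 at SD 3.5. Power for a one-point difference is then about 34% and 20% (normal approximation).

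**Effect of a difference in mix.** Inputs:
- SD of the difference 2.5 (section 4.1).
- Per-period SD σ of 2.5, 3.0 or 3.5. Section 4.1 says: "the GSK Treximet studies were parallel designs with standard deviations ranging from 2.5 to 3.5".
- Within-patient correlation ρ = 1 − 2.5²/(2σ²) = 0.50, 0.65, 0.74.
- 30 per sequence, no treatment effect, no carryover.
- Assumed: one sequence group is higher by δ in both periods, with δ = 0, 0.25, 0.5 or 0.75. Section 4.1 speaks of points. Reading them as hours is an inference from the lost-time formula in section 8.2.

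A shift of δ in both periods moves the sequence sums apart by 2δ and the first-period means by δ. It cancels from the within-patient differences. Simulating 200,000 trials per setting gives these rejection rates:

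| σ | δ | Carryover pretest | First period alone | Two-stage rule | Added by the shift (points) |
|---|---|---|---|---|---|
| 2.5 | 0 | 5.0% | 5.0% | 7.3% | – |
| 2.5 | 0.25 | 7.3% | 6.7% | 8.6% | 1.3 |
| 2.5 | 0.5 | 14.2% | 12.0% | 12.8% | 5.5 |
| 2.5 | 0.75 | 26.1% | 20.7% | 20.2% | 12.9 |
| 3.0 | 0 | 5.0% | 5.0% | 7.7% | – |
| 3.0 | 0.25 | 6.4% | 6.2% | 8.7% | 1.0 |
| 3.0 | 0.5 | 10.7% | 9.7% | 11.5% | 3.8 |
| 3.0 | 0.75 | 18.3% | 15.9% | 16.6% | 8.9 |
| 3.5 | 0 | 5.1% | 5.1% | 8.1% | – |
| 3.5 | 0.25 | 6.0% | 5.9% | 8.8% | 0.7 |
| 3.5 | 0.5 | 8.9% | 8.5% | 10.9% | 2.8 |
| 3.5 | 0.75 | 14.2% | 13.0% | 14.5% | 6.4 |

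The crossover contrast alone rejects in 4.9–5.1% in every setting.

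**How the two-stage rate arises.** With equal period variances, sums and differences are independent. The rate is therefore P(pretest significant) × P(first period significant, given that) + P(pretest not significant) × 0.05. For σ = 2.5 and δ = 0.5, the second term is 0.858 × 0.05 = 0.043, leaving 0.128 − 0.043 = 0.085 for the first. Dividing by 0.142 gives 0.60: once a chance or steered imbalance triggers the switch, about 60% of the resulting first-period tests are falsely significant.

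**The case against.** The strongest reply is that this is a crossover: "in the other arm of the study the same patients will treat 3 work day migraines with Treximet", just as they treat three with their usual triptan. Steering changes only the order, so the incentive is weak, and the default mixed model keeps its 5% error at every shift examined. Harm requires that staff use the list, that this shifts patient mix, and that the pretest is then significant. The documents give no evidence of the first two. All of this stands and limits the weight of the point.

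The excess with no shift, 7.3–8.1% against 5%, belongs to the pretest rule and not to the printed list. Dropping that rule would remove the WPAI inflation shown here even with the list public. That also stands, which is why the table separates the added part.

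The shifts are assumed. If staff sort by a median split on a severity cue that correlates 0.3–0.5 with a period's WPAI score, a shift of 0.25 needs 9–21% of enrolments steered, 0.5 needs 18–42%, and 0.75 needs 27–63%. The 0.75 rows are therefore an outer bound, and many entry criteria are factual and leave no room for choice. No figure was worked out for Migraine-ACT.

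Recruiting staff might have worked from a copy without Appendix 11.7. That cannot be excluded, but the plan does not say so.

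**Conclusion.** The concern holds. This is more than missing detail: followed as written, the plan makes every assignment knowable before consent and the eligibility decision. The within-patient treatment contrast is not at risk. The carryover test, the first-period WPAI comparison and the Migraine-ACT counterparts are.

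The realistic cost is the added error at shifts of 0.25 to 0.5: 0.7 to 5.5 percentage points on top of the pretest rule's own excess. This assumes a constant shift in both periods, normal data, two-sided tests and the SDs in section 4.1. Misuse is possible, not shown. The change should be made because it closes this route at very little cost.

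**What to change.** Take Appendix 11.7 out of the protocol. Deleting it is not enough, because the printed list is already known, so the statistics group should generate a new one and hold it away from enrolling staff. Release each sequence only after consent and confirmed eligibility are recorded, by numbered sealed envelopes or a call to the statistics group. Amend sections 4.4 and 5.3.1 to say so. If a safeguard of this kind already exists but is not written down, state it there.

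If patients have already entered, apply the new list to the remaining entries only, aiming for 30:30 overall, and report the change. An exact 30:30 total lets staff work out the last few assignments by counting, so a small departure is acceptable: a 32:28 split raises the variance of the crossover contrast by a factor of (1/32 + 1/28)/(2/30) = 1.004. Show baseline characteristics by sequence, but treat the table as descriptive. With 30 per group it would seldom reveal shifts of this size, and the flow chart collects no WPAI at Visit 1.

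The cost is a short amendment, one new list and a small release step at Visit 1, plus one table and a note in the report if enrolment has begun. Sample size and visits are unchanged. Concealment does not cure the pretest rule in section 8.2, which needs separate attention.

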5 STUDY DOSAGE/DOSAGE REGIMEN

5.1 INITIAL TREATMENT

Subjects will take a single dose of Treximet™ (1 tablet, which is 85mg of sumatriptan and 500mg of naproxen sodium) at headache onset, or Usual Triptan (at regular prescribed dose) to treat each of 3 migraines occurring during the work day.

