5.2 RESCUE TREATMENT

At 2 hours post-dose, if the subject has headache pain such that additional treatment is desired, subjects treating with their Usual Triptan will be permitted to take a second dose of their Usual Triptan, or their usual care rescue medication (however, no NSAIDS or other triptans would be permitted as a rescue treatment). For subjects treating with Treximet™, who have headache pain such that additional treatment is desired at 2 hours post dose, subjects may treat with a second Treximet™tablet or their usual care rescue medication (however, no NDAIDS or other triptans would be permitted as a rescue treatment). Subjects in both treatment arms may, at 24 hours post initial dose, take a second dose tablet, (if a second dose [usual triptan or Treximet™tablet] has not already been taken),when headache pain continues to require treatment. No more than 2 Treximet™ tablets are permitted to treat one migraine.

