2.3 Dosing in Patients with Hepatic Impairment

TREXIMET is contraindicated in patients with severe hepatic impairment [see *Contraindications (4)*, *Use in Specific Populations (8.7)*, *Clinical Pharmacology (12.3)*].

In patients with mild to moderate hepatic impairment, the recommended dosage in a 24-hour period is 1 tablet of TREXIMET 10/60 mg [see *Use in Specific Populations (8.7)*, *Clinical Pharmacology (12.3)*].

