8.7 Hepatic Impairment

TREXIMET is contraindicated in patients with severe hepatic impairment. For patients with mild or moderate hepatic impairment, the TREXIMET dose should be reduced. [*see Contraindications (4), Warnings and Precautions (5.15), Clinical Pharmacology (12.3)*].

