
Who should not take TREXIMET?**Do not take TREXIMET if you have:**

- heart problems, history of heart problems, or have ever had heart bypass surgery
- had a stroke, transient ischemic attack (TIAs), or problems with your blood circulation
- hemiplegic migraines or basilar migraines. If you are not sure if you have these types of migraines, ask your healthcare provider.
- narrowing of blood vessels to your legs and arms (peripheral vascular disease), stomach (ischemic bowel disease), or kidneys
- uncontrolled high blood pressure
- taken any medicines in the last 24 hours that are called 5-HT₁ agonists that are triptans or contain ergotamine. Ask your healthcare provider for a list of these medicines if you are not sure.
- taken an antidepressant medicine called a monoamine oxidase (MAO) inhibitor within the last 2 weeks. Ask your healthcare provider for a list if you are not sure.
- had an asthma attack, hives, or other allergic reaction with aspirin or any other NSAID medicine
- an allergy to sumatriptan, naproxen, or any of the ingredients in TREXIMET. See "What are the ingredients in TREXIMET?" below for a complete list of ingredients.
- third trimester of pregnancy
- liver problems

What should I tell my healthcare provider before taking TREXIMET?

Before you take TREXIMET, tell your healthcare provider about all of your medical conditions, including if you:

- have high blood pressure
- have high cholesterol
- have diabetes
- smoke
- are overweight
- have heart problems or a family history of heart problems or stroke
- have kidney problems
- have liver problems
- have had epilepsy or seizures
- are not using effective birth control
- are pregnant, think you might be pregnant, or are trying to become pregnant. **TREXIMET should not be used by pregnant women during the third trimester of their pregnancy.**
- are breastfeeding or plan to breastfeed. The components of TREXIMET pass into your breast milk and may harm your baby. Talk with your healthcare provider about the best way to feed your baby if you take TREXIMET.

Tell your healthcare provider about all the medicines you take, including prescription and over-the-counter medicines, vitamins, and herbal supplements.

TREXIMET and certain other medicines can affect each other, causing serious side effects.

How should I take TREXIMET?

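### Exclusion 10 can be read to admit a subject with known mild hepatic impairment, whom the protocol would dose at 85/500 mg although its appended label recommends 10/60 mg (minor patient-safety point)

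*Combined protocol and SAP*

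**What the plan says.** Section 4.3, item 10, excludes "subjects with a history of significant renal or hepatic disease". It gives no grade and does not define *significant*. No other numbered criterion concerns the liver. Section 3.1 adds a general condition, describing the patients as those "who have no contraindications to triptan or NSAID use".

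Section 5.1 sets the Treximet dose at "1 tablet, which is 85mg of sumatriptan and 500mg of naproxen sodium" for every subject. Section 5.2 permits a second tablet for the same attack from 2 hours after the first, or later: "Subjects in both treatment arms may, at 24 hours post initial dose, take a second dose tablet". Neither section makes a separate provision for hepatic impairment.

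The prescribing information in Appendix 11.6 is specific. Label section 2.3 states: "In patients with mild to moderate hepatic impairment, the recommended dosage in a 24-hour period is 1 tablet of TREXIMET 10/60 mg". Label section 8.7 agrees: "For patients with mild or moderate hepatic impairment, the TREXIMET dose should be reduced". Label sections 2.3 and 4 reserve the contraindication for severe impairment. The Medication Guide in the same appendix is stricter. Under the words "Do not take TREXIMET if you have" it lists liver problems with no grade attached. It also asks patients to tell their provider if they "have liver problems".

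**The concern.** The protocol fixes one dose, and its own appendix advises a much lower one for a group that the eligibility wording does not clearly keep out. A site could follow Sections 4.3 and 5.1 as written, enrol a subject whose history shows mild hepatic impairment, and give that subject 85/500 mg. Because the design is a crossover, allocation to either sequence does not avoid this: each subject who completes the study treats three attacks with Treximet.

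What is at stake is the safety of a possible few subjects. The power calculation and the treatment comparison are not in question.

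**Working it through.** **The plan's own figure.** Section 4.1 states 86% power for 60 subjects, a difference of 1 and an SD of the difference of 2.5. With two-sided alpha 0.05, the noncentrality is 1 / (2.5/√60) = 3.098. The noncentral t gives 86.2% with 59 degrees of freedom and 86.1% with 58, so the stated figure reproduces. It is used here only to price the fix.

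**Who gets past the criteria.** The provisions compare as follows.

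| Grade of known impairment | Section 4.3, item 10 | Section 3.1 (no contraindications) | Label dose | Dose under 5.1 |
|---|---|---|---|---|
| Severe | Excluded on any sensible reading | Excluded: contraindicated in label sections 2.3 and 4 | None | Not applicable |
| Moderate | Excluded on the natural reading | Not reached by label section 4 | 10/60 mg | 85/500 mg if admitted |
| Mild | Depends on how *significant* is read | Not reached by label section 4 | 10/60 mg | 85/500 mg if admitted |

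The gap is in the last row. Item 11 of the same list also uses *significant*, but then spells out in parentheses what it covers; item 10 does not. The flow chart in Section 6 lists a physical examination, a medical history and an eligibility check at Visit 1, and no liver test. Item 10, read against the history, is therefore the operative hepatic criterion.

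**Size of the dose difference.** Inputs: 85 and 500 mg per trial tablet (Section 5.1); 10 and 60 mg per labelled tablet (label section 2.3).

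- Sumatriptan: 85 / 10 = 8.5
- Naproxen sodium: 500 / 60 = 8.3

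Two trial tablets within 24 hours would give 170 / 10 = 17 and 1000 / 60 = 16.7. This is not the usual case. Section 5.3 dispenses three tablets for the initial dosing of three attacks, so a second tablet from that bottle uses up a later attack's first dose. If the second tablet is taken at 24 hours, which Section 5.2 also allows, the label's per-24-hour amount is no longer the matching comparison.

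**Exposure.** The only figure in the documents is in label section 12.3: sumatriptan AUC and Cmax about 70% higher in moderate impairment (8 patients, 8 matched healthy subjects). There is none for mild impairment.

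**The case against.** The strongest reply is that the risk is already covered. Item 10 bars significant liver disease in the history. The label is part of the protocol, and a clinician would naturally take *significant* to mean relevant to this drug; impairment that changes the labelled dose is relevant. There is one site, so divergent readings between sites do not arise, and a physician examines each subject at Visit 1. The Medication Guide adds a second stop: if the appendix may be cited for the defect, it may be cited for the safeguard. The 85/500 mg dose is itself the labelled adult dose (label section 2.1). The large ratios partly reflect that only two strengths are marketed.

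Much of this stands. It confines the point to mild impairment: with about 70% higher sumatriptan exposure, it would be strained to call moderate impairment not significant. It also makes the point minor. It does not remove it. Nothing in the protocol requires the protective reading or provides for a lower dose, and the Medication Guide is patient labelling, not an eligibility criterion. That the guide is stricter than item 10 is a reason to align the two.

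A reader might go further and infer that the protocol has no hepatic exclusion, that it would admit moderate impairment as a matter of course, or that subjects face a 17-fold overdose. The documents do not support these. An exclusion exists and is only ambiguous at its lower edge; moderate disease falls within it on the natural reading; and the 17-fold figure needs a second tablet within 24 hours.

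**Conclusion.** The point holds as a minor patient-safety ambiguity in item 10. A subject with known mild hepatic impairment can be admitted on one fair reading and would then receive, per tablet, 8.5 times the sumatriptan and 8.3 times the naproxen sodium that the appended label recommends. This rests on two things: that *significant* is read as leaving out mild impairment, and that the impairment is known from the history.

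The dose ratios should not be read as ratios of exposure or harm; the documents give no exposure figure for mild impairment. They also give no count of such subjects, and the number may be zero. Nor do they support any inference that the efficacy comparison is affected.

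**What to change.** Reword Section 4.3, item 10, to read: "subjects with a history of significant renal or hepatic disease", or any known hepatic impairment (mild, moderate or severe). This keeps the renal bar and the present hepatic bar, and adds the label's own grades so that any of them excludes. Apply it from the medical history already taken at Visit 1, and have a study physician confirm the wording.

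The change has limits. It adds no liver test, so it covers only known impairment. Neither the label nor the new wording sets criteria for the hepatic grades, so an isolated abnormal liver test would still need a clinical decision. The renal half of item 10 is left as it is.

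The cost is a one-line amendment with no new test, visit or drug supply, and possibly a very few otherwise eligible patients lost. The documents give no rate. Assuming 0 to 5% of 60, the loss is 0 to 3 subjects. If 3 were lost and not replaced, the noncentrality would be √57 / 2.5 = 3.020 and power would fall from 86.2% to 84.3% (n − 1 degrees of freedom; 86.1% to 84.3% with n − 2). If they were replaced, power would not change.
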